7 ANALYSIS SETS/ POPULATIONS

This study uses data from the MDV database, which includes the data used for both inpatient and outpatient insurance claims by hospitals according to the Diagnosis Procedure Combination (DPC) procedure. Japanese OAC treatment-naïve NVAF patients with who were prescribed apixaban, edoxaban or warfarin. Further information on patient selection and enrolment and follow-up time periods are included in Subsections 7.2 of the protocol.

7.1 FULL ANALYSIS SET

All eligible patients for the study will be included in the analysis.

Inclusion criteria

Patients must meet all of the following criteria to be eligible for the study:

- 1. Diagnosed with AF anytime in the baseline period or on the index date, also have definitive diagnosis of AF anytime in the baseline period, on the index date, or post-index period.*
- 2. Prescribed one of the index OACs (apixaban, edoxaban, or warfarin) on or after the day of AF diagnosis. The first observed prescription will be used to identify the patient's index date and treatment cohort*
- 3. No use of the any OACs during the baseline period (the 180 days before the index date)*
- 4. Age of 18 years or older on the index date.*

Exclusion criteria

Patients meeting any of the following criteria will not be included in the study:

- 1. Having a diagnosis of valvular atrial fibrillation, post-operative atrial fibrillation, rheumatic atrial fibrillation or mechanical-valvular atrial fibrillation during the baseline and post-index period*
- 2. Having a cardiac surgery procedure record during the baseline period*

3. *Having a joint replacement procedure record during the baseline period*
4. *Having a procedure of prosthetic heart valve during the baseline period*
5. *Having a diagnosis of venous thromboembolism during the baseline period*
6. *Female patients with pregnancy during the follow-up period*
7. *Patients prescribed “off-label” doses of OACs (per Japanese package insert of each OAC) or patients treated with OAC but in “off-label” or “contraindicated” manners.*

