7.2.1. Inclusion criteria

Patients must meet all of the following criteria to be eligible for the study:

1. Diagnosed with AF anytime in the baseline period or on the index date, also have definitive diagnosis of AF anytime in the baseline period, on the index date, or post-index period.
2. Prescribed one of the index OACs (apixaban, dabigatran, edoxaban, rivaroxaban or warfarin) on or after the day of AF diagnosis. The first observed prescription will be used to identify the patient's index date and treatment cohort
3. No use of the any OACs during the baseline period (the 180 days before the index date)
4. Age of 18 years or older on the index date.

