8.4 COVARIATES

We will use demographic and clinical information available at the index date and baseline period of the initiation prescription for apixaban, edoxaban, and warfarin cohorts.

Variable	Role	Operational definition
Sex Category	Baseline characteristic	Dichotomous variable equals 1 if sex is male and 2 if female
Age	Baseline characteristic	Age (in years) at the index date
Physician specialty	Baseline characteristic	Dichotomous variable equals 1 if a physician specialty on the index date is categorized into a cardiac specialty and 0 if others. Following specialties will be categorized as the cardiac specialty: cardiology stroke, cardiovascular surgery, pediatric cardiology, neurosurgery, cardiovascular medicine, and neurology. If there are ≥ 1 specialties but including the cardiac specialty, the physician specialty will be regarded as the cardiac specialty.
Hospital size (<500 beds or not)	Baseline characteristic	Dichotomous variable equals 1 if hospital size on the index date is <500 beds and 0 if ≥ 500 beds.
Hospitalization status on index date	Baseline characteristic	Dichotomous variable equals 1 if hospitalization status is inpatient and 0 if outpatient.
CHADS ₂	Baseline characteristic	CHADS ₂ score will be calculated based on age and the presence of congestive heart failure, hypertension, diabetes, and stroke or TIA.

CHA ₂ DS ₂ -VASC	Baseline characteristic	CHA ₂ DS ₂ -VASC score will be calculated based on age and the presence of congestive heart failure, hypertension, diabetes, stroke or TIA, vascular disease and sex category.
PT-INR (Prothrombin time-international normalized ratio)	Baseline period	Continuous variable. * Only available for patients treated with warfarin
Heart failure diagnosis in baseline	Baseline characteristic	Dichotomous variable equals 1 if there are ≥ 1 diagnoses for heart failure ICD-10 or disease codes during the baseline period.
Coronary heart disease diagnosis in baseline	Baseline characteristic	Dichotomous variable equals 1 if there are ≥ 1 diagnoses for coronary heart disease ICD-10 or disease codes during the baseline period.
Peripheral arterial disorder diagnosis in baseline	Baseline characteristic	Dichotomous variable equals 1 if there are ≥ 1 diagnoses for peripheral arterial disorder ICD-10 or disease codes during the baseline period.

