10 STATISTICAL METHODOLOGY AND STATISTICAL ANALYSES

10.1 STATISTICAL METHODS

10.1.1 Propensity Score Matching

In this study, matched cohorts (apixaban vs. warfarin, dabigatran versus warfarin, edoxaban vs. warfarin and rivaroxaban versus warfarin) will be created. Propensity scores will be estimated by unconditional logistic regression analyses that incorporate potential predictors of therapy as independent variables in the regression and cohort status as the outcome. The matching between warfarin group and each NOAC group (reference), 1:1 propensity score matching (PSM) method without replacement will be conducted. We will apply nearest neighbour method within caliper (width=0.2 times the standard deviation of the logit of the propensity score) matching technique. Standardized differences will be used to assess the balance of covariate between warfarin group and each NOAC group. If the standardized difference is less than 10%, the covariates are considered balanced. The following covariates will be included in the logistic regression:

- age on index date
- gender

- CHADS₂ score in baseline
- CHA₂DS₂-VASc score in baseline
- heart failure diagnosis in baseline
- coronary heart disease diagnosis in baseline
- peripheral arterial disorder diagnosis in baseline
- myocardial infarction diagnosis in baseline
- hyperthyroidism or thyrotoxicosis in baseline
- TIA diagnosis in baseline
- stroke or SE diagnosis in baseline
- renal dysfunction diagnosis in baseline
- liver dysfunction diagnosis in baseline
- bleeding diagnosis in baseline
- hypertension diagnosis in baseline
- diabetes mellitus diagnosis in baseline
- treated with antiplatelet drug in baseline
- treated with NSAIDs in baseline
- treated with gastric secretion inhibitor in baseline
- treated with statin-based drug in baseline
- treated with anti-hypertensives in baseline
- treated with anti-arrhythmics in baseline
- treated with beta-blockers in baseline
- treated with heparins in baseline
- cardioversion in baseline

The operational definitions for the above covariates are shown in the Section 6.4.

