10.1.5 Analysis of Categorical Data

Counts and percentages will be provided for dichotomous and polychotomous variables of baseline patient characteristics when performing descriptive analysis. Standardized differences will be calculated for each variable. For calculation of standardized differences, categorical variables will be converted into a set of binary indicators, one for each non-reference level of the variable and then a set of standardized differences defined⁶. In addition, the counts and percentages will be compared between patients treated with warfarin and patients treated with apixaban or edoxaban using chi-square tests.

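### SAP 7.1 limits eligibility to starters of apixaban, edoxaban or warfarin, contradicting the five-drug design in the protocol and in the rest of the SAP

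*SAP*

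**What the plan says.** SAP 7.1 opens its inclusion list with "Patients must meet all of the following criteria to be eligible for the study", so each item is binding. Item 2 is "Prescribed one of the index OACs (apixaban, edoxaban, or warfarin) on or after the day of AF diagnosis". Protocol 7.2.1 gives the same item as "Prescribed one of the index OACs (apixaban, dabigatran, edoxaban, rivaroxaban or warfarin) on or after the day of AF diagnosis".

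The shorter list is repeated in four other SAP sections:

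- SAP 7 describes the analysis population as patients "who were prescribed apixaban, edoxaban or warfarin".
- SAP 8.4 ties covariate collection to the "initiation prescription for apixaban, edoxaban, and warfarin cohorts".
- SAP 10.1.4 (continuous baseline data) compares warfarin with apixaban or edoxaban only.
- SAP 10.1.5 does the same for categorical data: "patients treated with warfarin and patients treated with apixaban or edoxaban using chi-square tests".

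Elsewhere the SAP is built on five drugs. Section 3 sets the index date and cohort from the first of five OACs. Section 4 names all five, and section 4.1 defines a dabigatran and a rivaroxaban cohort. Section 10.1.1 says "matched cohorts (apixaban vs. warfarin, dabigatran versus warfarin, edoxaban vs. warfarin and rivaroxaban versus warfarin) will be created". Every unredacted row of the 10.1.8 tables lists the four NOAC-warfarin pairs.

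**The concern.** The three-drug wording is not background text. Criterion 2 decides who enters the full analysis set and names the drugs whose first prescription fixes the index date and cohort. An analyst who takes eligibility from SAP 7.1 and covariates from SAP 8.4 would extract no dabigatran or rivaroxaban starters, and would have no covariates with which to fit their propensity scores. An analyst who works from SAP 10.1.1 and 10.1.8 needs both cohorts. A pre-specified plan should not give two answers to the question of who is eligible, least of all when an outside company carries out the analysis (protocol 7.8).

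**Working it through.** **1. Drugs admitted against drugs required**

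| Source | Apixaban | Dabigatran | Edoxaban | Rivaroxaban | Warfarin |
|---|---|---|---|---|---|
| Protocol 7.2.1 | yes | yes | yes | yes | yes |
| SAP 3, 4, 4.1 | yes | yes | yes | yes | yes |
| SAP 10.1.1, 10.1.8 | yes | yes | yes | yes | yes |
| SAP 7, 7.1 | yes | no | yes | no | yes |
| SAP 8.4 | yes | no | yes | no | yes |
| SAP 10.1.4, 10.1.5 | yes | no | yes | no | yes |

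NOACs required by SAP 10.1.1: {apixaban, dabigatran, edoxaban, rivaroxaban}, which gives the plan's own count of 4 comparisons. Drugs admitted by SAP 7.1: {apixaban, edoxaban, warfarin}. The first set minus the second is {dabigatran, rivaroxaban}. Hence 4 − 2 = 2 comparisons keep a NOAC cohort and 2 do not.

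**2. Baseline comparisons**

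Protocol 7.7 plans baseline tests across the warfarin and NOAC cohorts without leaving any out. SAP 10.1.4 and 10.1.5 apply the t-test, Mann-Whitney and chi-square tests to apixaban and edoxaban only. SAP 10.1.1 still requires standardised differences between warfarin and each NOAC group. The gap is therefore in the wording of the hypothesis tests in those two SAP sections, not in the balance assessment as a whole.

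**3. Index date**

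Take a patient whose first OAC is dabigatran, who then has more than 180 OAC-free days, and who next starts apixaban.

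- Under SAP 3 and protocol 7.1, the index prescription is dabigatran.
- Under SAP 7.1 read alone, dabigatran is not an index OAC, the 180-day washout in criterion 3 is met, and the patient could be indexed on apixaban.

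The difference arises only if SAP 3 is disregarded. The documents do not say how many patients have such a history.

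**4. Does the sample-size table depend on this?**

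SAP 6.2 gives requirements per group for a generic pairwise comparison. With events D = 4(z₀.₉₇₅ + z₀.₈₀)² / (ln HR)², rounded up, and N per group = D / [(1 − e^(−2r)) + (1 − e^(−2r·HR))], where r is the yearly control rate, I assumed 2 years of follow-up (SAP 6.2 states none; 10.1.3 uses two years as primary) and no dropout. At r = 0.012:

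| HR | D | N computed | N in SAP 6.2 |
|---|---|---|---|
| 0.6 | 121 | 121 / (0.02371 + 0.01430) = 3,183 | 3,166 |
| 0.7 | 247 | 247 / (0.02371 + 0.01666) = 6,118 | 6,083 |
| 0.8 | 631 | 631 / (0.02371 + 0.01902) = 14,767 | 14,683 |

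All 12 cells reproduce to within 3%. No input depends on which NOACs are eligible, so correcting criterion 2 leaves the table as it is.

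**The case against.** The strongest reply is that the five-drug intent is plain and that anyone running the analysis would see the slip.

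- SAP 2 says that italic text comes directly from the protocol. Criterion 2 is in italics, so it presents itself as protocol text, and the protocol has five drugs.
- SAP 4 and SAP 7 both send the reader to protocol 7.2 for patient selection.
- Protocol 7.7 lets the SAP modify the protocol's plans, but says that major changes to primary endpoint definitions or analyses would appear in a protocol amendment. The protocol's amendment table is empty, and its revision history lists only a schedule change.
- Protocol 7.5 describes the preceding study (CER2) with exactly this three-drug list, which makes carried-over text a plausible cause. That is an inference.

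Most of this stands. A reader might infer that the SAP deliberately dropped dabigatran and rivaroxaban, and the documents do not support that. In practice an analyst following SAP 10.1.1 and 10.1.8 would probably notice two missing cohorts and raise a query, so silent loss of results is unlikely.

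The reply does not remove the contradiction. SAP 7.1 restates the eligibility rule in full, with a different content from the text it claims to copy, and four other sections agree with the wrong version. The SAP contains no statement of which passage prevails.

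**Conclusion.** The contradiction is real and should be corrected. Its secure size is 2 of 4 planned comparisons without a NOAC cohort if SAP 7.1 is applied literally, plus two SAP sections that omit the same two cohorts from the baseline tests. The literal reading is the assumption on which this rests.

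Three stronger conclusions a reader might draw go beyond the documents:

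- *A fixed count of lost primary tests.* With major bleeding and stroke/SE as the primary outcomes, 2 drugs × 2 outcomes gives 4 of 8. But SAP 8.2 calls any bleeding secondary while SAP 10.1.8 labels it primary, and on the latter reading the count is 2 × 3 = 6 of 12. Only the proportion, one half, is stable.
- *No baseline comparison planned for the two cohorts.* Protocol 7.7 and SAP 10.1.1 do plan for them.
- *Misassigned index dates as an established effect.* SAP 3 already indexes on the first of all five OACs. The effect is conditional on ignoring that section, and it cannot be quantified from the documents.

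**What to change.** Replace criterion 2 in SAP 7.1 with the protocol 7.2.1 text: all five OACs, with the index date at the first observed prescription of any of them, as SAP 3 already has it. Extend the population statement in SAP 7, the covariate statement in SAP 8.4 and the baseline comparisons in SAP 10.1.4 and 10.1.5 to all four NOAC cohorts. The cost is SAP wording only. No analysis method, endpoint or sample-size figure changes. The correction belongs before the cohort extraction is programmed.

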7.2 SAFETY ANALYSIS SET

Bleeding events will be collected for this analysis. As mentioned above, bleeding will be investigated as safety-related primary endpoints. However, other adverse event, serious AE or non-serious AE will not be collected in this analysis because the dataset provided by MDV will not contain the AE-related information.

7.3 OTHER ANALYSIS SET

None.

CCI

CCI

8 ENDPOINTS AND COVARIATES

8.1 EFFICACY/ EFFECTIVENESS ENDPOINT(S)

Variable	Role	Operational definition
Stroke/SE (composite) event after index date	Outcome (primary endpoint)	Operational definition of Stroke and SE will follow the operational definition of Stroke event after index date and SE event after index date. Time to events will be defined as the number of days from the index date to the occurrence of the first stroke or SE.
Ischemic stroke event after index date	Outcome (secondary endpoint)	Ischemic stroke after index date not including the index date will be identified using hospital claims which had an ischemic stroke diagnosis code as the first listed ICD-10 diagnosis code (Appendix, Table 5). An event occurrence of ischemic stroke is defined as a case that "01: Disease name which input the most medical resources", "02:Sub-disease name", "11: Main disease name", "21: Disease name behind hospitalization", or "31: Disease name which input the second most medical resources" in DPC database. Time to ischemic stroke will be defined as the number of days from the index date to the occurrence of the first ischemic stroke.
Hemorrhagic stroke event after index date	Outcome (secondary endpoint)	Hemorrhagic stroke after index date not including the index date will be identified using hospital claims which had a hemorrhagic stroke diagnosis code as the first listed ICD-10 diagnosis code (Appendix, Table 5). An event occurrence of hemorrhagic stroke is defined as a case that "01: Disease name which input the most medical resources", "02:Sub-disease name", "11: Main disease name", "21: Disease name behind hospitalization", or "31: Disease name which input the second most medical resources" in DPC database. Time to hemorrhagic stroke will be defined as the number of days from the index date to the occurrence of the first hemorrhagic stroke.
SE event after index date	Outcome (secondary endpoint)	SE after index date not including the index date will be identified using hospital claims which had a SE diagnosis code as the first listed ICD-10 diagnosis code (Appendix, Table 5). An event occurrence of SE is defined as a case that "01: Disease name which input the most medical resources", "02:Sub-disease name",

Variable	Role	Operational definition
		"11: Main disease name", "21: Disease name behind hospitalization", or "31: Disease name which input the second most medical resources" in DPC database. Time to SE will be defined as the number of days from the index date to the occurrence of the first SE event.

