6.2 STATISTICAL DECISION RULES

All statistical tests will be performed at $p=0.05$ (two-sided) with no adjustment for multiplicity.

Based on results of Japanese sub-population in confirmatory trials for NOACs, the required sample size to detect a significant difference in stroke/SE was calculated. The following sample size calculation is based on the significance level of 0.05 (two-sided) and power of 80%.

Desired Power	Hazard Ratio	Event Rate (Control)	Required Sample Size per Group
0.8	0.6	1.2 %/year	3,166
		1.6 %/year	2,378
		2.1 %/year	1,815
		2.6 %/year	1,469

Desired Power	Hazard Ratio	Event Rate (Control)	Required Sample Size per Group
	0.7	1.2 %/year	6,083
		1.6 %/year	4,570
		2.1 %/year	3,488
		2.6 %/year	2,823
	0.8	1.2 %/year	14,683
		1.6 %/year	11,031
		2.1 %/year	8,422
		2.6 %/year	6,817

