10.1.3 Analysis of Time-to-Event Data

Time-to-endpoints will be summarized by OAC with the number and percentage of patients with event, and event rates. Event rates will be calculated as the number of patients with event per 100 patient-years at risk. In addition, total patient-years will be presented for each OAC.

Patients who experience a clinical endpoint event after the earlier of their discontinuation of the index OAC, switching from the index OAC, withdrawal from the database, or the end of intended follow-up period (i.e., two years after the index date as primary and one year for a sensitive analysis) will be censored.

Patients who do not experience a clinical endpoint event will be censored at the earlier of their discontinuation of the index OAC, switching from the index OAC or withdrawal from the database will be censored.

Propensity score matching

See above

Cox proportional hazards model

Cox proportional hazards model will be used to compare endpoints in each of the propensity-score-matched cohorts, with robust sandwich estimates to account for the clustering within matched sets. The Cox proportional hazards model will include only index OAC treatment as the independent variable if patient characteristics are balanced between groups based on standardized difference in components of the PS. If not balanced, the unbalanced variable will be also included to the model in addition to the index OAC treatment. The hazard ratios with corresponding 95% confidence intervals and p-values will be reported.

CCI

Kaplan-Meier Method

For each endpoint, Kaplan-Meier curves will be plotted for the time from the index date to first event by index OAC treatment in each of the propensity-score-matched cohorts. The log-rank test is used for comparison between two curves.

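### The primary stroke/SE definition has no event-date or new-admission rule, so a stroke from a stay already open on the index date can count as an outcome

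*SAP*

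**What the plan says.** SAP 8.1 defines each component of the primary effectiveness endpoint in the same way. For ischemic stroke the rule begins "Ischemic stroke after index date not including the index date will be identified using hospital claims which had an ischemic stroke diagnosis code". The code must be first listed, and a case qualifies if it sits in any of five DPC fields: 01, 02, 11, 21 or 31. Field 02 is a sub-disease name and the last is "31: Disease name which input the second most medical resources". Time to event runs from the index date to the occurrence, which is not tied to any date in the claim. The protocol is no tighter: its section 7.3 asks for at least one stroke or SE code during follow-up, and section 7.9 says diagnoses are not adjudicated.

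Four other provisions bear on this:
- **Inpatient starts are eligible.** SAP 8.4 records status on the index date: "Dichotomous variable equals 1 if hospitalization status is inpatient and 0 if outpatient".
- **Recent stroke is not an exclusion** (protocol 7.2.2, SAP 7.1). It enters the propensity model in SAP 10.1.1 as "stroke or SE diagnosis in baseline".
- **Follow-up begins the day after the index date** (protocol 7.1, SAP 3), with no lag and no discharge condition.
- **Hospitalization status on the index date is absent from the propensity list** in SAP 10.1.1.

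**The concern.** Take a patient admitted with a stroke who is first prescribed an anticoagulant during that stay. The stay carries the stroke code, and follow-up opens the next day while the patient may still be in hospital. The written rule removes only what is dated on or before the index date. If the analyst dates a DPC diagnosis by discharge, by claim month or by any other point later than admission, the stroke that preceded treatment becomes an early outcome event on that treatment.

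True events are rare, so a small number of carried-over strokes matters. Equal carry-over in the two arms pulls a real difference toward a hazard ratio of 1 and costs power. Unequal carry-over can create or hide a difference.

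A second fault sits in the same definition. A first-listed requirement and the acceptance of fields 02 and 31 cannot both hold, so two programmers could build different primary endpoints.

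**Working it through.** **1. The plan's own figure.** SAP 6.2 says "the required sample size to detect a significant difference in stroke/SE was calculated", with "significance level of 0.05 (two-sided) and power of 80" per cent. Allocation is from SAP 10.1.1: "1:1 propensity score matching (PSM) method without replacement". Section 6.2 gives no follow-up time; two years is taken from SAP 10.1.3 ("two years after the index date as primary and one year for a sensitive analysis"). No dropout is applied.

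Schoenfeld events: D = 4(1.96 + 0.8416)² / (ln HR)². For HR 0.6, D ≈ 120. At a control rate of 1.2%/year over two years the event probabilities are 1 − exp(−0.024) = 0.0237 and 1 − exp(−0.0144) = 0.0143, mean 0.0190. N per group = 120.3 / 0.0190 / 2 ≈ 3,166, the stated value. All 12 cells of the table agree within 1.2%. One-year follow-up gives 6,299 for this cell, about twice the stated number. The table is therefore sound; it assumes that every counted event is a true one.

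**2. Effect on the hazard ratio, equal carry-over.** No carry-over figure is in the documents. Assumptions: share f = 4% of both arms starts during a stroke stay; a share q of those stays is dated after index; mean follow-up is one year. The control rate, 2.1 per 100 patient-years, is one of the SAP 6.2 values.

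Observed HR = (0.021 × HR + f·q) / (0.021 + f·q), with true HR 0.70:
- q = 0 (dated by admission): 0.70, no effect.
- q = 0.1: (0.0147 + 0.004) / (0.021 + 0.004) = 0.75.
- q = 0.5: (0.0147 + 0.020) / (0.021 + 0.020) = 0.85.

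With a two-year mean follow-up the base term doubles to 0.042: 0.0334/0.046 = 0.73 and 0.0494/0.062 = 0.80.

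**3. Effect on power.** Let c be the proportion of each arm whose index-stay stroke is counted (f·q above runs from 0 to 2%). Over two years, with control rate λ, observed HR = [2λ·HR − ln(1 − c)] / [2λ − ln(1 − c)], and power = Φ(½√D·|ln HR| − 1.96) with D the counted events. For HR 0.6, 1.2%/year, N = 3,166 per group:

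| c | Events counted | Observed HR | Power |
|---|---|---|---|
| 0 | 120 | 0.60 | 80% |
| 0.25% | 136 | 0.64 | 75% |
| 0.5% | 151 | 0.67 | 70% |
| 1% | 182 | 0.72 | 61% |
| 2% | 245 | 0.78 | 48% |

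At c = 1%, about 62 of 182 counted events (34%) are false, and restoring 80% power takes about 4,967 per group. For HR 0.8, 2.1%/year, N = 8,422, c from 0.25% to 2% gives an observed HR of 0.81 to 0.87 and power of 77% to 61%. These are approximations, because carried-over events cluster early and the hazards would not be proportional.

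**4. Unequal carry-over, true HR 1.00.** With the step 2 formula, f = 5% for warfarin and 3% for the NOAC: q = 0.1 gives 0.024/0.026 = 0.92 and q = 0.5 gives 0.036/0.046 = 0.78. Reversed, 1.08 and 1.28. With the step 3 formula at 1.6%/year, c = 1% for warfarin against 0.5% for the NOAC gives 0.0370/0.0421 = 0.88; reversed, 1.14.

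**The case against.** The strongest reply is that the definition speaks of a stroke occurring after the index date. A stroke that caused the admission happened on or before it, and if diagnoses are dated by admission none leaks. That is a fair reading of intent. It does not settle the matter, because the SAP never states the dating convention and the program will need one. Carry-over is possible, not shown.

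A reader might infer that the five DPC fields cause the carry-over. They do not: field 21, the reason for admission, would carry the same stroke for the index stay. Cutting the fields down would not close the gap, and the first-listed conflict neither causes nor prevents it.

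A reader might also infer that carry-over is unbalanced between arms. The documents do not show that. Baseline stroke, heparin use and two scores that include stroke are all in the propensity model, and SAP 10.1.3 adds any unbalanced propensity component to the Cox model. The 5% against 3% scenario would by itself give a standardized difference of 0.02/0.196 = 10.2%, just over the 10% limit, unless older strokes offset it. What remains is that the baseline stroke covariate pools a current stroke with one months old. Inpatient status is also not a propensity component, so its imbalance would not trigger adjustment. Balance is not assured.

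Protocol 7.9 acknowledges misclassification in general terms only. Redacted text might hold a related sensitivity analysis, but the primary definition in SAP 8.1 is fully visible.

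**Conclusion.** The point holds as a gap in the definition of a primary endpoint: no date rule, no new-admission requirement, and a field specification that contradicts itself. It does not establish that index strokes will be counted, nor in which direction the result would move.

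The size runs from zero, if diagnoses are dated by admission, to a shift of a true HR from 0.70 to 0.75-0.85 under the equal carry-over assumptions in step 2 (0.73-0.80 if mean follow-up is two years). In the SAP row for HR 0.6 and 1.2%/year, carry-over of only 0.5% per arm would lower power from 80% to 70%. Every carry-over proportion is an assumption; the documents give neither the number of inpatient starters with a current stroke nor the mean follow-up. The correction should be made before the analysis because the endpoint is primary and the change is cheap.

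**What to change.** - **SAP 8.1, primary analysis:** state the date that places an event, and count stroke/SE only from a hospitalization whose admission date is after the index date. Diagnoses on a stay already open on the index date do not count.
- **SAP 8.1, fields:** replace the first-listed requirement plus five fields with one stated DPC field set.
- **SAP 8.2:** apply the same admission rule only to the hospitalization-based major bleeding endpoints. Extending it to any bleeding would discard outpatient bleeds and largely collapse that endpoint into major bleeding.
- **Sensitivity analyses:** report the stroke/SE result without the admission restriction, and the result excluding patients who were inpatients on the index date.

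The cost is SAP wording and programming, assuming admission dates can be obtained from the database. The downside is that a true new stroke during the index stay is not counted in the primary analysis. The documents do not allow that loss to be quantified; the unrestricted sensitivity analysis bounds it.
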